6.10.5 Qualitative analyses

Reach will be assessed as participation and attrition bias. We will assess intervention uptake by CGM sensor usage.

The interview/focus group data will be analysed qualitatively using a thematic framework approach (55-57). These analyses will be conducted primarily by members of the qualitative research team. We will explore relationships between the patient reported outcomes (anxiety, depression, diabetes distress, glucose monitoring satisfaction), maternal glucose outcomes (CGM TIR, HbA1c) and participants engagement with CGM and antenatal care (CGM sensor usage, antenatal clinic visits).

Interview transcripts will be transcribed verbatim; transcripts that require translation will be back translated to ensure accuracy and quality. Patient and HCP data will be analysed and reported separately. Data will be managed in NVIVO v12[™].

6.10.6 Within-trial economic analysis

A within-trial economic evaluation will be conducted, based on an NHS cost perspective with a 28-day horizon beyond birth. Resource use associated with both the CGM intervention and standard care will be measured (including diabetes treatment, nurse intervention, CGM sensor and reader device/phone, and SMBG meter, lancets, and test strips) along with maternal/baby hospital care e.g., antenatal visits, duration of hospitalization and neonatal care unit admission. We will collect data on outpatient consultations, medications, and maternal inpatient admissions and length of stay. All resource use data will be costed using national databases such as the National Schedule of Reference costs.

The primary outcome measure of the health economics analysis will be incremental cost per qualityadjusted life year (QALY). The health-related quality of life instrument EQ-5D-5L collected at baseline and 32 weeks' gestation will provide maternal utility values for the calculation of QALYs. The valuation of EQ-5D-5L responses will follow the latest guidance from NICE's manual for health technology evaluation. Additionally, costs will also be assessed in relation to the primary outcomes of maternal glucose (costs per 5% increase in CGM TIR) and neonatal care admission or death (stillbirth/neonatal death).

A Health Economic Analysis Plan will be produced prior to the outcome analysis, where the incremental cost and incremental effect for trial outcomes associated the CGM intervention, compared to standard SMBG testing, will be estimated. To assess value for money, assuming dominance does not occur (where one option is more effective and less costly than the other option), the incremental cost-effectiveness ratio associated with the CGM intervention will be estimated for each outcome and assessed in relation to available cost-effectiveness thresholds e.g., £20,000-£30,000 per QALY 58. The associated level of uncertainty will also be characterised by using bootstrapping and by estimating the cost-effectiveness acceptability curve and by conducting sensitivity analysis.

The cost utility analysis comparing CGM with SMBG will be performed under the intention-to-treat principle. An NHS and personal social care perspective and a societal perspective will be adopted. If applicable, the results of the economic evaluation will also be presented using a cost-consequence analysis framework where the primary, selected secondary outcomes and costs from each trial arm will be presented in a disaggregated manner over the trial period.

We will report descriptive statistics for resource use, costs, and EQ-5D-5L utilities at each follow-up time point using complete data. We will estimate differences in cost and utilities between trial arms using mixed effects linear regression models to allow for multiple follow-ups clustered within participants. Missing data will be addressed using best practice in cost-effectiveness studies. We will undertake mean imputation of baseline data and multiple imputation of follow-up costs and of EQ-5D values, if appropriate after examining the patterns of missing data. We will use predictive mean matching to create a total number of imputed datasets as the proportion of data missing across all time periods.

Following multiple imputation, we will estimate the total costs and QALYs for each participant in the trial. On each imputed dataset, we will estimate incremental costs and QALYs using separate linear regression models controlling for treatment allocation and other variables. These estimates will be combined using Rubin's rule to produce the mean difference in costs and QALYs of CGM relative to SMBG. Incremental cost-effectiveness ratio (ICER) will be estimated by dividing the difference in costs by the difference in QALYs of CGM and SMBG with results depicted on the cost-effectiveness plane. This will be interpreted as the additional costs/savings associated to the additional QALY benefits from CGM compared to SMBG. The joint uncertainty around incremental costs and QALYs will be estimated using bootstrapping from each imputed dataset, running the estimation models and extracting the estimated treatment effects. This will allow capturing the correlation between the two treatment effects (on costs and QALYs) and estimate the probability of CGM being cost-effective at a maximum willingness to pay of £20,000 to £30,000 per QALY gained. This will be calculated by estimating the proportion of bootstrap replicates with a net monetary benefit (NMB) above 0 for each threshold value, where the NMB is obtained by the product of the mean difference in QALYs and the threshold value minus the mean difference in costs.

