Importantly, MATERNAL GLUCOSE is the KEY MODIFIABLE RISK FACTOR for neonatal morbidity and death (2, 5). National audit data reported 565 serious adverse outcomes in EOT2D mothers with above-target glucose compared to 105 in T2D mothers with in-target glucose levels. Serious neonatal morbidity (neonatal unit admissions >24 hour) and mortality are significantly reduced in babies of mothers who achieved target glucose levels (HbA1c <43 mmol/mol) after 24 weeks' gestation (5).

Neonatal care admissions separate mothers and babies, with immediate and longer-term consequences for maternal wellbeing, mother-baby bonding, and infant feeding. The average neonatal care admission in EOT2D pregnancy is 5 days, which at £9,463.70 (£1,892.74 daily) is a major cost burden for the NHS (9).

WHY IS THIS RESEARCH IMPORTANT NOW?

1) Understanding whether diabetes technology can improve pregnancy outcomes was the number one James Lind Alliance (JLA) Priority Setting Partnership (PSP) priority for diabetes pregnancy research(10). Listening to the priorities of pregnant women is particularly pertinent following the Ockenden report, where many women, especially from ethnic minorities and poorer communities reported poor experiences...*I felt frightened and not listened to*..." (9, 11, 12).

2) The burden of EOT2D pregnancy is high(2), and rapidly increasing with gestational diabetes (GDM) affecting one in seven women, half of whom will develop EOT2D within 5 years (7).

3) Nearly ONE in TWO BABIES born to mothers with EOT2D have serious health complications (birth defects, neonatal care admissions or death) with major impacts for women, families and the NHS(2, 5). We know that many adverse outcomes are potentially preventable by improving maternal glucose (2, 3, 13).

4) There are stark healthcare inequalities in access to diabetes technology. Currently, <15% of mothers with EOT2D (ethnically diverse, higher BMI, more deprived) are offered continuous glucose monitoring (CGM) compared to >90% of mothers with T1D (predominantly white, lower BMI, more affluent). Recent NICE guidance (31/03/22) highlighted the urgent need to address health inequalities in CGM access. Addressing inequalities by bringing high quality research to under-served communities is also a key NIHR priority.

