5) The complications associated with EOT2D pregnancy carry high societal costs (pregnancy loss, stillbirth, neonatal death) and high NHS costs (preeclampsia £4656, neonatal care admission £9463 for 5-days, neonatal death £767)(14, 15).

Our study will examine whether real-time CGM is a viable tool to improve maternal glucose levels and reduce serious neonatal morbidity (neonatal care admissions or death) in EOT2D pregnancy.

REVIEW OF EXISTING EVIDENCE

National audit data confirm that background rates of neonatal morbidity and death are high (42.2% and 6.7%, respectively) during EOT2D pregnancy (2, 5, 16). However, they can be reduced if women achieve target glucose levels after 24 weeks' gestation. This is traditionally done by adjusting diabetes treatment (diet, insulin, metformin) according to 4-7 daily 'finger-prick' self-monitored blood glucose (SMBG) tests. Our Patient and Public Involvement (PPI) partners confirmed that many pregnant women find glucose testing extremely burdensome; *"having to monitor my bloods every single day was really tough" – "sneaking off into the toilet to do my sugars - it takes up so much time just thinking about it, planning it around meals and work"*. SMBG also provides only limited glucose information, collected using unreliable methods (paper diaries), on which to adjust diabetes treatments.

CGM technology, which measures interstitial glucose from a device worn day and night, is revolutionizing how glucose levels are monitored and managed. Compared to HbA1c or finger-prick SMBG, CGM gives detailed information (1,440 glucose measures/day), describing glucose changes across the 24-hour day. Sensors, the size of a 1p coin, typically worn on the back of the arm, send interstitial glucose readings via Bluetooth, directly to a mobile phone (17, 18). CGM enables the user to assess how much time they spend in, above and below the target glucose range and alerts them if their glucose is too high or too low. Patients hold their CGM Time In Range (TIR) glucose information

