on their mobile phones. They find glucose TIR information engaging because it provides immediate feedback on any changes they make to their diet or diabetes treatments (19, 20)⁻(21). The patient-centredness of TIR is strongly endorsed by a survey of 3,461 people with diabetes (70% with T2D) who ranked TIR as the factor, which after food choices, has the biggest impact on their daily lives. In contrast to SMBG, CGM data are easily shared remotely with the users, carers and health care professional (HCP) teams allowing diabetes treatment plans (diet, metformin, insulin) to be more precisely adjusted (22-25). This is especially relevant during pregnancy where there are frequent changes in gestational physiology and pharmacokinetics requiring timely personalized treatment adjustments (26, 27).

We performed an international randomised controlled trial (RCT) of CGM use in T1D pregnancy (CONCEPTT)(28). We demonstrated that compared to finger-prick SMBG, CGM use was associated with improved maternal glucose levels with higher CGM Time In Range (TIR) during the third trimester. It was changes in CGM TIR (68% vs 61%; p=0·0034) and neonatal health outcomes [large for gestational age (LGA) birthweight odds ratio 0·51, 95% CI 0·28 to 0·90; p=0·0210, neonatal unit admission >24h odds ratio 0·48; CI 0·26 to 0·86; p=0·0157, neonatal hypoglycaemia 0·45; CI 0·22 to 0·89; p=0·0250), 1-day shorter neonatal hospital stay (p=0·0091)] that led to changes in NICE guidelines and accelerated NHS implementation (Dec 2020)(29). Providing CGM in T1D pregnancy dominated management with finger-prick SMBG, by being less expensive and more effective(14, 15). For maternal outcomes, CGM use was clinically and cost effective. For neonatal outcomes, CGM cost less (-£2,612) while being more effective (QALYs 75.4 vs. 73.8) making it cost-saving with an incremental cost-effective ratio (ICER) of *minus* £1,571/QALY gained. This was driven, almost exclusively, by fewer neonatal admissions (14).

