6.5.2 Secondary outcomes

Biomedical maternal:

- HbA1c and CGM mean glucose, glucose management indicator (GMI), frequency and duration of glycaemic excursions [%Time-Above-Range (>6.7 & >7.8 mmol/L), %Time-Below-Range (<3.5 & <3.0 mmol/L)], glycaemic variability (glucose SD, CV)]
- 2) Hypertensive disorders
- 3) Gestational weight gain (from initial antenatal visit to 36 weeks' gestation)
- 4) Diabetes treatment (metformin and insulin use)
- 5) Hospital admissions and duration of stay
- 6) Severe hypoglycaemia, hyperosmolar hyperglycaemic state, and diabetic ketoacidosis episodes

Biomedical neonatal:

- 1) Gestational age at birth
- 2) Mode of delivery
- Birth weight for gestational age (SDS) (GROW customised birth weight, LGA birth weight >90th centile or SGA <10th centile)
- 4) Neonatal care unit admission (duration of stay, highest level care)
- 5) Adverse events (pregnancy loss <24 weeks, congenital anomaly (any), stillbirth, neonatal death)
- 6) Birth injury (spinal cord injury, clavicular, skull or long bone fracture, shoulder dystocia, nerve palsy, subdural or intracerebral haemorrhage confirmed by computerized tomography (CT) or magnetic resonance imaging (MRI) scan, hypoxic ischaemic encephalopathy)
- 7) Neonatal morbidity (treatment for neonatal hypoglycaemia; treatment for respiratory distress; treatment for neonatal jaundice)
- 8) Feeding at hospital discharge (exclusive breast-feeding / partial breast-feeding / exclusive formula feeding)

Patient-reported outcome measures (PROMs):

Diabetes distress, anxiety and depression and treatment satisfaction using short questionnaires at baseline (except for GMSS which is applicable only in late pregnancy) and 32 weeks' gestation:

- T2D Distress Scale (DDS)
- Glucose Monitoring Satisfaction Survey (GMSS)
- Patient Health Questionnaire 9-item depression scale (PHQ-9)
- Generalized Anxiety Disorder 7-item scale (GAD-7)
- EQ-5D-5L (maternal)

The nested qualitative study will also explore the acceptability, barriers, facilitators as well as patient and HCP support needs for CGM use in T2D pregnancy.

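### The primary cost-per-QALY analysis counts the baby's hospital costs but takes QALYs only from the mother, so a stillbirth or neonatal death carries no QALY loss

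*Protocol*

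**What the plan says.** All references are to the protocol.

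- **Primary economic measure.** Section 6.10.6: "The primary outcome measure of the health economics analysis will be incremental cost per" QALY.
- **Costs.** The same section measures the resources used by CGM and by standard care, "along with maternal/baby hospital care e.g., antenatal visits, duration of hospitalization and neonatal care unit admission". The evaluation is "based on an NHS cost perspective with a 28-day horizon beyond birth".
- **QALYs.** The EQ-5D-5L at baseline and 32 weeks' gestation "will provide maternal utility values for the calculation of QALYs". Section 6.5.5 says the same, and section 6.5.2 lists the instrument for the mother only.
- **Decision rule.** Section 6.10.6 feeds this cost and QALY pair into the ICER, into a net monetary benefit (threshold × QALY difference, minus cost difference) and into the probability of cost-effectiveness at £20,000 to £30,000 per QALY.
- **Other economic analyses.** Costs are also set against TIR and against neonatal admission or death. A cost-consequence presentation is planned conditionally, and a Health Economic Analysis Plan is still to be written.

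No infant utility, infant life-years or QALY loss for a perinatal death is mentioned. Yet stillbirth and neonatal death are part of the primary neonatal outcome (section 6.5.1).

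**The concern.** Costs cover two people and QALYs cover one. A baby who is stillborn generates no neonatal unit cost, and the loss of that baby does not reduce QALYs. If CGM prevents deaths, the added survivors bring neonatal costs and no QALYs. The last utility is measured at 32 weeks, so the mother's own loss of quality of life after a later stillbirth or a neonatal death is not measured either.

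At stake is the meaning of the headline cost per QALY and of the acceptability curve. A decision maker would read both as summarising the trial's health effects, while one component of the neonatal primary outcome has zero weight in the QALYs.

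**Working it through.** **Inputs**
- Neonatal admission: 5 days at £1,892.74 per day; neonatal death £767 (section 5.1: "neonatal care admission £9463 for 5-days, neonatal death £767").
- Neonatal admission rate 42.2% in control and 26.0% planned under CGM (section 6.7); 211 women per arm.
- Threshold λ of £20,000 to £30,000 per QALY; NMB = λ × ΔQALY − Δcost (section 6.10.6).
- Assumptions: no neonatal unit cost for a stillbirth; £767 is the full cost of a neonatal death apart from unit days; 42.2% is the admission rate among live births.

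**1. The plan's own figure.** 5 × £1,892.74 = £9,463.70, as stated.

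**2. Effect of one death on cost, with QALYs unchanged**
- Average live birth: 0.422 × £9,463.70 = £3,994. A stillbirth lowers cost by this amount on average. The saving is £9,464 against an admitted survivor and £0 against a baby never admitted.
- Neonatal death with no unit days: £3,994 − £767 = £3,227 saved. The saving is used up after £3,227 / £1,892.74 = 1.7 unit days, after which the death raises cost. Against an admitted survivor, this takes (£9,463.70 − £767) / £1,892.74 = 4.6 days.
- Infant QALYs lost in the planned ratio: 0 in every case.

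**3. Effect on the comparison of arms, all else equal**
- Four extra stillbirths among 211 women (1.9 points): 4 × £3,994 / 211 = £76 lower mean cost, equal to £76 / £20,000 = 0.0038 QALY.
- For scale, an assumed maternal utility gain of 0.02 to 0.05, building linearly over 16 to 20 weeks, gives 0.5 × 0.02 × 16/52 = 0.003 to 0.5 × 0.05 × 20/52 = 0.010 QALY. The two are of the same order.

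**4. Set against the planned admission effect**
- (0.422 − 0.260) × £9,463.70 = £1,533 lower mean cost per woman.
- To match that through stillbirths alone would take £1,533 / £3,994 = 38 percentage points more deaths, or 16.2 points if every death replaced an admitted survivor.

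**5. QALY loss per stillbirth at which the sign changes**
- Against an average live birth: £3,994 / £30,000 = 0.13 and £3,994 / £20,000 = 0.20 QALY.
- Against an admitted survivor: £9,464 / £30,000 = 0.32 and £9,464 / £20,000 = 0.47 QALY.
- Infant QALYs limited to 28 days, at an assumed utility of 1, reach at most 28 / 365.25 = 0.077. That is below every break-even value, so the infant loss has to run beyond 28 days to have the right sign.

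**The case against.** A reader might infer that the arm with more deaths will look more cost-effective, or that the ratio ignores the neonatal primary outcome. The documents support neither.

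- The first holds only if admissions, other costs and maternal QALYs are equal between arms. Under the planned effect the admission saving of £1,533 per woman is far larger than any plausible effect of deaths on cost.
- The second overlooks that neonatal admissions are costed. They supply 42.2 of the 48.8 points in the control composite (Table 1). What is missing is a QALY weight for death.
- Not every death saves money, as the 1.7-day figure shows.
- The protocol applies an odds ratio of 0.48 to admissions and to the composite, never to deaths alone, so it gives no projected fall in deaths to build on.
- The type 1 diabetes model cited in section 5.1 did report neonatal QALYs (75.4 against 73.8). However, the protocol gives no loss per death from it and attributes its result almost wholly to admissions. It offers no value to copy.

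It can also be said that the cost per admission-or-death analysis, the possible cost-consequence table and the unwritten Health Economic Analysis Plan cover the gap. They cover it in part. The first two show deaths as harm, but the first weighs an admission and a death equally, the second is conditional, and neither changes the primary ratio or its curve. The later plan does not settle it, because the protocol already names the QALY source and the NMB formula.

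The strongest point that stands concerns precision. At an assumed 20 to 25 QALYs per death, one chance death among 211 women moves an arm's mean by 20/211 = 0.095 to 25/211 = 0.118 QALY. That is worth about £1,900 to £3,600 per woman across the two thresholds, more than the whole planned admission saving. This argues against letting an externally valued joint analysis replace the planned curve.

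**Conclusion.** The mismatch is in the text and holds. Baby costs enter the primary ratio, infant QALYs do not, and a perinatal death has no weight on the QALY side. All else equal, a stillbirth moves net monetary benefit towards the arm where it occurs, by about £3,994 per event against an average live birth, and deaths prevented by CGM earn no credit. A reversal of the ratio is not expected under the planned admission effect. The £3,994 rests on the costing assumptions listed with the inputs. That no QALYs are lost follows from the protocol alone.

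**What to change.** In section 6.10.6 and the Health Economic Analysis Plan:

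1. Report the maternal cost-utility ratio with maternal costs only, so that costs and QALYs cover the same people.
2. Prespecify a mother-plus-baby scenario, with its own net monetary benefit and acceptability curve, that assigns a stated QALY loss to each stillbirth and neonatal death. Show it over a range and let the loss extend beyond the 28-day horizon. Present it beside the planned curve, not in its place.

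The cost is wording and some analysis work. Stillbirths and neonatal deaths are already collected (section 6.6.1.9). There are two drawbacks: the loss per death is an external assumption, and the scenario will be imprecise because a few deaths can dominate it. Both should be stated with the result.

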6.10.7 Analysis of tissue samples

Blood samples will be taken at 4 collection points (baseline, 28 weeks', 32 weeks' and 36 weeks' gestation) for local lab measurement of HbA1c levels.

In addition, a sample will be taken and transferred to the Norwich Biorepository for metabolic phenotyping (assessment of maternal baseline pancreatic function: C-peptide and islet cell antibodies).

A laboratory manual will be developed.

6.11 Data monitoring

6.11.1 Data Monitoring Committee

Further details of the roles and responsibilities of the Data Monitoring Committee (DMC), including membership, relationships with other committees, decision making processes, and the timing and frequency of interim analyses (and description of stopping rules and/or guidelines where applicable) are described in detail in the PROTECT DMC Terms of Reference (ToR).

6.11.2 Interim analyses

There will be no formal interim analyses however the following will be reviewed at the end of the internal pilot phase:

- CGM sensor usage (i.e. percentage time spent using CGM)
- Availability of CGM glucose data for the primary maternal outcome
- Event rate for the neonatal composite outcome

6.11.3 Data monitoring for harm

Adverse events will be collected as per section 7 and analysed according to the Statistical Analysis Plan. Serious Adverse Events (SAEs) by treatment group will be reviewed by the DMC as described in their terms of reference.

6.11.4 Quality assurance and control

6.11.4.1 Risk assessment

The Quality Assurance (QA) and Quality Control (QC) considerations for the PROTECT trial are based on the standard NCTU Quality Management Policy that includes a formal Risk Assessment, and that acknowledges the risks associated with the conduct of the trial and proposals of how to mitigate them through appropriate QA and QC processes. Risks are defined in terms of their impact on: the rights and safety of participants; project concept including trial design, reliability of results and institutional risk; project management; and other considerations.

QA is defined as all the planned and systematic actions established to ensure the trial is performed and data generated, documented and/or recorded and reported in compliance with the principles of GCP and applicable regulatory requirements. QC is defined as the operational techniques and activities performed within the QA system to verify that the requirements for quality of the trial related activities are fulfilled.

